## 1. RCT Details

This section provides a high-level overview of the RCT that the described real-world evidence study is trying to replicate as closely as possible given the remaining limitations inherent in the healthcare databases.

### 1.1 Title

**Liraglutide and Cardiovascular Outcomes in Type 2 Diabetes ([LEADER](#) trial)**

### 1.2 Intended aim(s)

The primary hypothesis was that liraglutide would be noninferior to placebo (plus standard of care) with regard to the primary outcome, with a margin of 1.30 for the upper boundary of the 95% confidence interval of the hazard ratio.

### 1.3 Primary endpoint for replication and RCT finding

Composite of Cardiovascular Death, Non-fatal Myocardial Infarction, or Non-fatal Stroke

### 1.4 Required power for primary endpoint and noninferiority margin (if applicable)

90% power and noninferiority margin of hazard ratio of 1.30

### 1.5 Primary trial estimate targeted for replication

HR = 0.87 (95% CI 0.78-0.97) comparing liraglutide to placebo (Marso et al.)

## 2. Person responsible for implementation of replication in Aetion

[name]. implemented the study design in the Aetion Evidence Platform. S/he is not responsible for the validity of the design and analytic choices. All implementation steps are recorded and the implementation history is archived in the platform.

[figure not shown]
## 3. Data Source(s)

United/Optum, MarketScan, Medicare

#### 4. Study Design Diagram

The study design diagram visualizes key aspects of the longitudinal study design for expedited review.

##### Design Diagram – LEADER TRIAL REPLICATION

## 5. Cohort Identification

### 5.1 Cohort Summary

This study will involve a new user, parallel group, cohort study design comparing liraglutide to the DPP4 inhibitor (DPP4i) antidiabetic class as a proxy for placebo. Both 2nd generation sulfonylureas (SUs) and DPP4is are not known to have an impact on the outcome of interest. The comparison against DPP4i is the **primary comparison**. Initiators of 2nd generation SUs are used as a secondary comparator group. The patients will be required to have continuous enrollment during the baseline period of 180 days before initiation of liraglutide or a comparator drug (cohort entry date). Follow-up for the outcome (3P-MACE), begins the day after drug initiation. As in the trial, patients are allowed to take other antidiabetic medications during the study.

### 5.2 Important steps for cohort formation

#### 5.2.1 Eligible cohort entry dates

Market availability of liraglutide in the U.S. started on January 20, 2010.

- For Marketscan: January 20, 2010-Dec 31, 2017 (end of data availability).
- For Medicare: Jan 1, 2012-Dec 31, 2017 (start- end of data availability).
- For Optum: January 20, 2010-March 31, 2019 (end of data availability).

#### 5.2.2 Specify inclusion/exclusion criteria for cohort entry and define the index date

Inclusion and exclusion criteria were adapted from the trial as closely as possible. Definitions for all inclusion/exclusion are provided in **Appendix A** and are summarized in the flowcharts below.

### 5.3 Flowchart of the study cohort assembly

- For Liraglutide vs DPP4i

	Optum		Marketscan		Medicare*	
	Less Excluded Patients	Remaining Patients	Less Excluded Patients	Remaining Patients	Less Excluded Patients	Remaining Patients

All patients in the database		74,864,884		191,990,035		23,466,175
Patients who used exposure or a reference between 20 January 2010 to Dec 2017 (for Marketscan)/March 2019 (for Optum) and 01 January 2012-December 2017 for Medicare	-74,012,464	852,420	-190,638,745	1,351,290	-21,492,649	1,973,526
Patients who have continuous 6 months registration in the database	-111,929	740,491	-134,586	1,216,704	-516,146	1,457,380
Patients without prior use of reference	-394,596	345,895	-710,577	506,127	-754,558	702,822
Patients without prior use of exposure	-112,350	233,545	-193,164	312,963	-102,088	600,734
Excluded because patient qualified in >1 exposure category	-75	233,470	-138	312,825	-48	600,686
Patients who did not have missing age information	-10	233,460	0	312,825	0	600,686
Patients who did not have missing gender information	-16	233,444	0	312,825	0	600,686
Excluded based on Inclusion 1- DM Type 2	-10,665	222,779	-29,308	283,517	-4,803	595,883
Excluded based on Inclusion 3- Either Prior cardiovascular disease cohort or No Prior cardiovascular disease group	-42,768	180,011	-98,418	185,099	-17,351	578,532
Excluded based on Exclusion 1- Type 1 diabetes	-3,952	176,059	-4,538	180,561	-14,315	564,217
Excluded based on Exclusion 2- Use of GLP1 or Pramlintide or DPP4i within 3 months prior to index	-953	175,106	-963	179,598	-1,652	562,565
Excluded based on Exclusion 3-Long Acting Insulin in prior 90 days	-7,143	167,963	-5,629	173,969	-21,421	541,144
Excluded based on Exclusion 4-Diabetic ketoacidosis in prior 90 days	-112	167,851	-84	173,885	-359	540,785
Excluded based on Exclusion 5- An acute coronary or cerebrovascular event in the previous 14 days	-546	167,305	-720	173,165	-1,764	539,021
Excluded based on Exclusion 7- Oxygen canister use as a proxy for NYHA class IV	-286	167,019	-297	172,868	-1,919	537,102
Excluded based on Exclusion 8- Current continuous renal replacement therapy/ESRD	-437	166,582	-333	172,535	-2,110	534,992
Excluded based on Exclusion 10- Liver disease	-2,572	164,010	-1,845	170,690	-7,745	527,247
Excluded based on Exclusion 11- Organ Transplant	-83	163,927	-107	170,583	-188	527,059
Excluded based on Exclusion 12- History of Malignant Neoplasm in previous 5 years and Exclusion 13- Family or personal history of multiple endocrine neoplasia type 2 (MEN2) or familial medullary thyroid carcinoma (FMTC)	-5,878	158,049	-5,403	165,180	-24,286	502,773
Excluded based on Exclusion 14- Personal history of non-familial medullary thyroid carcinoma	0	158,049	0	165,180	0	502,773
Excluded based on Exclusion 17- Drug abuse or dependence	-450	157,599	-164	165,016	-878	501,895
Excluded based on Exclusion 20- Contraception or pregnancy	-357	157,242	-511	164,505	-1002	500,893

Final cohort	157,242	164,505	500,893
--------------	---------	---------	---------

\* Medicare database includes only patients with at least one diagnosis for diabetes, heart failure, or cerebrovascular disease.

- For Liraglutide vs 2nd Gen. SUs

	Optum		MarketScan		Medicare*	
	Less Excluded Patients	Remaining Patients	Less Excluded Patients	Remaining Patients	Less Excluded Patients	Remaining Patients
All patients in the database		74,864,884		191,990,035		23,466,175
Patients who used exposure or a reference between 20 January 2010 to Dec 2017 (for MarketScan)/March 2019 (for Optum) and 01 January 2012-December 2017 for Medicare	-73,337,305	1,527,579	-189,889,741	2,100,294	-19,968,954	3,497,221
Patients who have continuous 6 months registration in the database	-204,156	1,323,423	-233,189	1,867,105	-952,050	2,545,171
Patients without prior use of reference	-888,112	435,311	-1,294,078	573,027	-1,703,970	841,201
Patients without prior use of exposure	-103,834	331,477	-177,643	395,384	-95,982	745,219
Excluded because patient qualified in >1 exposure category	-138	331,339	-236	395,148	-85	745,134
Patients who did not have missing age information	-14	331,325	0	395,148	0	745,134
Patients who did not have missing gender information	-26	331,299	0	395,148	0	745,134
Excluded based on Inclusion 1- DM Type 2	-24,242	307,057	-58,280	336,868	-10,070	735,064
Excluded based on Inclusion 3- Either Prior cardiovascular disease cohort or No Prior cardiovascular disease group	-62,008	245,049	-130,017	206,851	-24,553	710,511
Excluded based on Exclusion 1- Type 1 diabetes	-4,763	240,286	-5,243	201,608	-15,909	694,602
Excluded based on Exclusion 2- Use of GLP1 or Pramlintide or DPP4i within 3 months prior to index	-7,666	232,620	-8,727	192,881	-23,001	671,601
Excluded based on Exclusion 3-Long Acting Insulin in prior 90 days	-6,604	226,016	-5,151	187,730	-19,399	652,202
Excluded based on Exclusion 4-Diabetic ketoacidosis in prior 90 days	-169	225,847	-151	187,579	-442	651,760
Excluded based on Exclusion 5- An acute coronary or cerebrovascular event in the previous 14 days	-806	225,041	-1,218	186,361	-2,112	649,648
Excluded based on Exclusion 7- Oxygen canister use as a proxy for NYHA class IV	-3,508	221,533	-2,257	184,104	-3,451	646,197

Excluded based on Exclusion 8- Current continuous renal replacement therapy/ESRD	-710	220,823	-674	183,430	-3,666	642,531
Excluded based on Exclusion 10- Liver disease	-3,303	217,520	-2,124	181,306	-9,653	632,878
Excluded based on Exclusion 11- Organ Transplant	-105	217,415	-143	181,163	-263	632,615
Excluded based on Exclusion 12- History of Malignant Neoplasm in previous 5 years and Exclusion 13- Family or personal history of multiple endocrine neoplasia type 2 (MEN2) or familial medullary thyroid carcinoma (FMTC)	-7,050	210,365	-6,342	174,821	-28,690	603,925
Excluded based on Exclusion 14- Personal history of non-familial medullary thyroid carcinoma	0	210,365	0	174,821	0	603,925
Excluded based on Exclusion 17- Drug abuse or dependence	-638	209,727	-226	174,595	-1119	602,806
Excluded based on Exclusion 20- Contraception or pregnancy	-371	209,356	-453	174,142	-967	601,839
Final cohort		209,356		174,142		601,839

\* Medicare database includes only patients with at least one diagnosis for diabetes, heart failure, or cerebrovascular disease.

## 6. Variables

### 6.1 Exposure-related variables:

#### Study drug:

The study exposure of interest is initiation of liraglutide. Initiation will be defined by no use of liraglutide or a comparator in the prior 6 months before treatment initiation (washout period).

#### Comparator agents:

- Initiators of liraglutide will be compared to initiators of-
  - DPP4i (**primary**)
  - 2nd generation sulfonylureas

Because liraglutide and comparators are frequently used as second or third line treatments of T2DM, we expect it to be unlikely that liraglutide and comparators are initiated in patients with substantially different baseline risk for proposed outcomes.

### 6.2 Preliminary covariates:

- Age
- Sex
- Combined Comorbidity Index (CCI), measured over the default baseline covariate assessment period, defined as 180 days prior to and including index date

Covariates listed above represent only a small subset of covariates that will ultimately be controlled for in the design and analysis. We use the covariates above only for initial feasibility analyses to judge whether there is likely to be sufficient overlap between treatment groups to proceed with the study. Remaining covariates are defined only after the study has passed the initial feasibility analysis and the initial power assessment and are listed in Table 1 (**Appendix B**). These covariates are based on those used by Patorno et al. (2019).

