## 9. Balance Assessment after PS matching

Action report name:

- For Liraglutide vs 2nd Gen. SUs

Optum: <https://bwh-dope.aetion.com/projects/details/632/results/44783/result/0>

Marketscan: <https://bwh-dope.aetion.com/projects/details/633/results/45436/result/0>

Medicare: <https://bwh-dope.aetion.com/projects/details/634/results/45432/result/0>

- For Liraglutide vs DPP4i

Optum: <https://bwh-dope.aetion.com/projects/details/632/results/44786/result/0>

Marketscan: <https://bwh-dope.aetion.com/projects/details/633/results/44787/result/0>

Medicare: <https://bwh-dope.aetion.com/projects/details/634/results/45433/result/0>

Date conducted: 11/18/2019 (Medicare 11/30/2019)

After review of initial feasibility and power analyses, complete creation of the remaining covariates (see Table 1 below for list of covariates). Again, using the dummy outcome of a 90-day gap in database enrollment, complete a 1:1 PS-matched analysis. The PS should include the complete list of covariates (excluding laboratory values, which are missing in some patients).

- Provide plot of PS distributions stratified by treatment group.

Note- Please refer to **Appendix B**.

- Report covariate balance after matching.

Note- For Table 1, please refer to **Appendix B**.

- Report reasons for censoring by treatment group.

- For Liraglutide vs DPP4i

	Overall	Referent	Exposure
Dummy Outcome	0 (0.00%)	0 (0.00%)	0 (0.00%)
Death	1,271 (0.75%)	827 (0.98%)	444 (0.53%)
Start of an additional exposure	4,700 (2.79%)	1,913 (2.27%)	2,787 (3.30%)

End of index exposure	99,981 (59.27%)	45,078 (53.44%)	54,903 (65.09%)
Specified date reached	29,951 (17.76%)	16,708 (19.81%)	13,243 (15.70%)
End of patient enrollment	22,798 (13.51%)	12,483 (14.80%)	10,315 (12.23%)
Switch to other SUs (for censoring) + nursing home admission	9,989 (5.92%)	7,336 (8.70%)	2,653 (3.15%)

- For Liraglutide vs 2nd Gen. SUs

	Overall	Referent	Exposure
Dummy Outcome	0 (0.00%)	0 (0.00%)	0 (0.00%)
Death	858 (0.79%)	595 (1.10%)	263 (0.49%)
Start of an additional exposure	4,294 (3.96%)	967 (1.78%)	3,327 (6.14%)
End of index exposure	61,038 (56.33%)	27,098 (50.01%)	33,940 (62.64%)
Specified date reached	21,830 (20.15%)	13,222 (24.40%)	8,608 (15.89%)
End of patient enrollment	14,181 (13.09%)	7,902 (14.58%)	6,279 (11.59%)
Switch to other SUs (for censoring) + nursing home admission	6,163 (5.69%)	4,398 (8.12%)	1,765 (3.26%)

- Report follow-up time by treatment group.

- For Liraglutide vs DPP4i

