Internal medicine/family medicine visits (30 days prior); n (%)	94,520 (68.7%)	11,561 (59.4%)	94,848 (66.2%)	12,851 (61.1%)	290,265 (63.8%)	25,156 (56.2%)	479,633 (65.2%)	49,568 (58.1%)	0.15		
Internal medicine/family medicine visits (31 to 180 days prior); n (%)	110,003 (79.9%)	14,957 (76.9%)	111,872 (78.0%)	16,418 (78.0%)	347,879 (76.5%)	34,444 (76.9%)	569,754 (77.4%)	65,819 (77.2%)	0.00		
Cardiologist visit; n (%)	45,210 (32.8%)	6,781 (34.8%)	45,236 (31.6%)	7,080 (33.6%)	177,196 (39.0%)	16,264 (36.3%)	267,642 (36.4%)	30,125 (35.3%)	0.02		
Number of Cardiologist visits (30 days prior); n (%)	17,032 (12.4%)	2,281 (11.7%)	16,404 (11.4%)	2,355 (11.2%)	67,756 (14.9%)	5,177 (11.6%)	101,192 (13.8%)	9,813 (11.5%)	0.07		
Number of Cardiologist visits (31 to 180 days prior); n (%)	38,027 (27.6%)	5,824 (29.9%)	38,469 (26.8%)	6,074 (28.9%)	152,067 (33.4%)	14,293 (31.9%)	228,563 (31.1%)	26,191 (30.7%)	0.01		
Electrocardiogram; n (%)	49,482 (35.9%)	6,621 (34.0%)	54,504 (38.0%)	7,572 (36.0%)	181,062 (39.8%)	15,773 (35.2%)	285,048 (38.7%)	29,966 (35.1%)	0.07		
Use of glucose test strips; n (%)	6,117 (4.4%)	808 (4.2%)	5,867 (4.1%)	1,004 (4.8%)	17,314 (3.8%)	1,728 (3.9%)	29,988 (4.0%)	3,540 (4.2%)	-0.01		
Dialysis; n (%)	82 (0.1%)	11 (0.1%)	136 (0.1%)	9 (0.0%)	560 (0.1%)	18 (0.0%)	778 (0.1%)	0.08 (0.0%)	0.04		
Naïve new user v8; n (%)	23,724 (17.2%)	2,950 (15.2%)	23,744 (16.6%)	2,590 (12.3%)	66,532 (14.6%)	4,828 (10.8%)	114,000 (15.5%)	10,368 (12.2%)	0.10		
N antidiabetic drugs at index date											
...mean (sd)	2.12 (0.81)	2.07 (0.88)	0.06	2.14 (0.81)	2.10 (0.90)	0.05	2.10 (0.79)	2.11 (0.85)	-0.01	2.11 (0.80)	2.10 (0.87)
...median (IQR)	2.00 [2.00, 3.00]	2.00 [1.00, 3.00]	0.00	2.00 [2.00, 3.00]	2.00 [1.00, 3.00]	0.00	2.00 [2.00, 3.00]	2.00 [1.00, 3.00]	0.00	2.00 (0.80)	2.00 (0.87)
number of different/distinct medication prescriptions											
...mean (sd)	10.45 (4.75)	11.70 (5.14)	-0.25	10.12 (4.59)	11.57 (4.91)	-0.31	10.69 (4.75)	11.32 (4.71)	-0.13	10.53 (4.72)	11.47 (4.86)
...median (IQR)	10.00 [7.00, 13.00]	11.00 [8.00, 15.00]	-0.20	9.00 [7.00, 13.00]	11.00 [8.00, 14.00]	-0.42	10.00 [7.00, 13.00]	11.00 [8.00, 14.00]	-0.21	9.81 (4.72)	11.00 (4.86)
Number of Hospitalizations											
...mean (sd)	0.14 (0.46)	0.10 (0.36)	0.10	0.15 (0.43)	0.10 (0.35)	0.13	0.22 (0.61)	0.11 (0.40)	0.21	0.19 (0.55)	0.11 (0.38)

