...median (IQR)	0.00 [0.00, 1.00]	0.00 [0.00, 1.00]	0.00	0.00 [0.00, 1.00]	0.00 [0.00, 1.00]	0.00	0.00 [0.00, 1.00]	0.00 [0.00, 1.00]	0.00	0.00 (1.60)	0.00 (1.34)
Number of HbA1c tests ordered											
...mean (sd)	1.35 (0.93)	1.40 (0.92)	-0.05	0.98 (0.94)	1.15 (0.95)	-0.18	1.44 (0.91)	1.53 (0.88)	-0.10	1.33 (0.92)	1.41 (0.91)
...median (IQR)	1.00 [1.00, 2.00]	1.00 [1.00, 2.00]	0.00	1.00 [0.00, 2.00]	1.00 [0.00, 2.00]	0.00	1.00 [1.00, 2.00]	1.00 [1.00, 2.00]	0.00	1.00 (0.92)	1.00 (0.91)
Number of glucose tests ordered											
...mean (sd)	0.60 (2.85)	0.57 (1.41)	0.01	0.43 (1.50)	0.50 (1.20)	-0.05	0.49 (1.20)	0.51 (1.13)	-0.02	0.50 (1.69)	0.52 (1.22)
...median (IQR)	0.00 [0.00, 0.00]	0.00 [0.00, 1.00]	0.00	0.00 [0.00, 0.00]	0.00 [0.00, 1.00]	0.00	0.00 [0.00, 1.00]	0.00 [0.00, 1.00]	0.00	0.00 (1.69)	0.00 (1.22)
Number of lipid tests ordered											
...mean (sd)	1.08 (1.01)	1.08 (1.01)	0.00	0.86 (1.31)	1.00 (1.31)	-0.11	1.07 (0.86)	1.11 (0.88)	-0.05	1.03 (0.99)	1.08 (1.03)
...median (IQR)	1.00 [0.00, 2.00]	1.00 [0.00, 2.00]	0.00	1.00 [0.00, 1.00]	1.00 [0.00, 1.00]	0.00	1.00 [0.00, 2.00]	1.00 [0.00, 2.00]	0.00	1.00 (0.99)	1.00 (1.03)
Number of creatinine tests ordered											
...mean (sd)	0.06 (0.35)	0.06 (0.30)	0.00	0.06 (0.35)	0.06 (0.34)	0.00	0.09 (0.39)	0.10 (0.41)	-0.02	0.08 (0.38)	0.08 (0.37)
...median (IQR)	0.00 [0.00, 0.00]	0.00 [0.00, 0.00]	0.00	0.00 [0.00, 0.00]	0.00 [0.00, 0.00]	0.00	0.00 [0.00, 0.00]	0.00 [0.00, 0.00]	0.00	0.00 (0.38)	0.00 (0.37)
Number of BUN tests ordered											
...mean (sd)	0.04 (0.28)	0.03 (0.23)	0.04	0.04 (0.29)	0.04 (0.27)	0.00	0.06 (0.32)	0.06 (0.32)	0.00	0.05 (0.31)	0.05 (0.29)
...median (IQR)	0.00 [0.00, 0.00]	0.00 [0.00, 0.00]	0.00	0.00 [0.00, 0.00]	0.00 [0.00, 0.00]	0.00	0.00 [0.00, 0.00]	0.00 [0.00, 0.00]	0.00	0.00 (0.31)	0.00 (0.29)
Number of tests for microalbuminuria											
...mean (sd)	0.82 (1.23)	0.87 (1.25)	-0.04	0.52 (0.99)	0.64 (1.07)	-0.12	0.49 (0.73)	0.56 (0.77)	-0.09	0.56 (0.90)	0.65 (0.97)
...median (IQR)	0.00 [0.00, 2.00]	0.00 [0.00, 2.00]	0.00	0.00 [0.00, 1.00]	0.00 [0.00, 1.00]	0.00	0.00 [0.00, 1.00]	0.00 [0.00, 1.00]	0.00	0.00 (0.90)	0.00 (0.97)
Total N distinct ICD9/ICD10 diagnoses at the 3rd digit level											
...mean (sd)	5.98 (8.59)	7.00 (8.44)	-0.12	2.59 (5.59)	2.39 (4.66)	0.04	6.46 (9.71)	6.21 (8.58)	0.03	5.62 (8.84)	5.45 (7.76)

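### The propensity score has no socioeconomic or preventive-care covariate in any database and no race in Optum or MarketScan, and the death counts in the matched arms warn of residual confounding

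*Combined protocol and SAP*

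**What the plan says.** Section 6.2 names age, sex and a comorbidity index for the feasibility stage and adds that "Covariates listed above represent only a small subset of covariates that will ultimately be controlled for in the design and analysis". That sentence is not an error; it defers to the final list, which is in Appendix B: "Remaining covariates are defined only after the study has passed the initial feasibility analysis and the initial power assessment and are listed in Table 1". Section 9 then fixes what is modelled: "The PS should include the complete list of covariates (excluding laboratory values, which are missing in some patients". Table 1 minus laboratory values is therefore the whole of the confounding control. Both analyses in Section 13 (the matched Cox model and the trimmed model adjusted for score deciles) draw on it.

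On the expected size of the problem, Section 6.1 (Comparator agents) states that "we expect it to be unlikely that liraglutide and comparators are initiated in patients with substantially different baseline risk for proposed outcomes". The target in Section 1.5 is "HR = 0.87 (95% CI 0.78-0.97) comparing liraglutide to placebo".

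**The concern.** Patients who start a newer injectable drug may be better off, better insured and more engaged in preventive care than those who start an older oral one. Such traits could lower cardiovascular events and death whatever the drug does, and would push the hazard ratio below 1. Balance on listed covariates does not show whether unlisted ones are balanced. The target effect is a 13% reduction (1 - 0.87), so a residual bias of a few percent could decide whether the replication appears to succeed.

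Deaths matter here because the composite does not use cause of death. Appendix A implements the primary outcome as inpatient mortality, MI or stroke, with the vital status file for Medicare and discharge codes for the commercial data. Linked cardiovascular mortality comes later, for secondary analyses only. A confounded difference in all-cause death would pass straight into the primary hazard ratio.

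**Working it through.** **1. What Table 1 holds.** Care-seeking and lifestyle proxies are present: "Number of HbA1c tests ordered", "Number of lipid tests ordered", microalbuminuria tests, glucose test strips, office, primary-care and specialist visits, electrocardiograms, statins, smoking, obesity and frailty scores. Absent in all three databases: income, subsidy or dual eligibility, plan or coverage type, area deprivation, vaccination, cancer screening. Region is the only geographic item. Race is N/A for Optum and MarketScan.

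**2. Medicare race (DPP4i comparison).** Standardised difference = (p1 - p2)/sqrt((p1q1 + p2q2)/2), comparator v liraglutide.
- Before matching, White 337,843/454,700 = 74.3% v 38,225/44,778 = 85.4%: -0.278 (printed -0.28). Asian 0.227 (printed 0.22), Hispanic 0.165 (0.16), Black 0.104 (0.10).
- After matching, White 85.8% v 85.3%: 0.014. Every printed race difference is 0.02 or less in size, in the sulfonylurea cohort as well.

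**3. Reach of the missing commercial race (Section 10).**
- Pairs: (19,187 + 20,777)/84,345 = 47%.
- Events: (548.7 + 503.2)/(548.7 + 503.2 + 3,426.2) = 1,052/4,478 = 23%. The denominator is the sum of the three database panels. The pooled panel's 3,655.5 uses an unweighted mean risk, (14.30 + 12.11 + 38.60)/3 = 21.67.
- Assumed scenario: the unmatched Medicare imbalance (non-White 25.7% v 14.6%) carries over in full to the commercial data, with an assumed risk ratio R for the trait. Bias factor = (1 + 0.146(R - 1))/(1 + 0.257(R - 1)). Pooled factor = that value raised to the power 0.235.

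| R (assumed) | Commercial databases | Pooled |
|---|---|---|
| 1.2 | 0.979 | 0.995 |
| 1.5 | 0.951 | 0.988 |
| 2.0 | 0.912 | 0.979 |
| 3.0 | 0.853 | 0.963 |

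**4. Deaths in the matched cohorts (Section 9 censoring tables).** The printed figures reproduce: 444/84,345 = 0.53% v 827/84,345 = 0.98%, and 263/54,182 = 0.49% v 595/54,182 = 1.10%. The censoring rows sum to 168,690 and 108,364, twice the number of pairs.
- DPP4i: crude ratio 444/827 = 0.537. Median follow-up ratio, liraglutide over comparator: Optum 148/173 = 0.855; MarketScan and Medicare 159/209 = 0.761. Rate ratio 0.537/0.855 = 0.63 to 0.537/0.761 = 0.71. With patient-weighted medians (156.5/200.8 = 0.779) it is 0.69; the 95% factor is exp(1.96 x sqrt(1/444 + 1/827)) = 1.12, giving 0.61-0.77.
- Sulfonylureas: crude ratio 263/595 = 0.442. Follow-up ratios 148/181 = 0.818 and 148/231 = 0.641 give 0.54 to 0.69; the weighted value is 0.66 (0.57-0.76).
- For follow-up alone to bring the DPP4i ratio to 1, liraglutide person-time would have to be 0.54 of the comparator's. The printed medians give 0.76-0.86.

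**5. A check on covariates left out of the score.** In the matched sulfonylurea cohort, pooled laboratory values still differ: HbA1c 8.10 v 7.86 (0.13), total cholesterol 0.13, LDL 0.12, glucose 0.12, all lower with liraglutide. About 80% of commercial patients lack these values. The DPP4i cohort is closer (Optum HbA1c 0.01, LDL 0.09).

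**The case against.** Four counter-arguments carry weight.

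- **Healthy-user control is not absent.** A reader might infer from the missing screening items that nothing addresses care-seeking. Table 1 shows otherwise, and matching works on those items: in the DPP4i cohort the HbA1c, lipid and microalbuminuria test counts differ by at most 0.01, test strips by 0.01 and endocrinologist visits by 0.04. The gap is narrower: preventive services and socioeconomic position.
- **Medicare race is handled.** The pre-match difference of 0.28 might be read as uncontrolled channelling. It is removed by the match, and the scenario above suggests that missing commercial race cannot account for the death gap.
- **The death gap is not proof.** It is tempting to note that 0.61-0.77 lies wholly below the trial's lower limit of 0.78 and call the cohort confounded. That limit belongs to the three-point composite, whereas these are all-cause deaths counted as a censoring reason and not split by database. Censoring also differs by arm: the row that includes nursing home admission is 8.70% v 3.15%, and end of index exposure 53.4% v 65.1%. A drug effect is possible too. The follow-up correction is rough, because arm-level medians are printed identically for MarketScan and Medicare although the overall medians differ (185 v 179 days for DPP4i, 168 v 179 for sulfonylureas).
- **Measured imbalance says little about unmeasured.** Pooled age (0.65), dementia (0.23) and hospitalization (0.17) differ before matching, so the Section 6.1 expectation looks optimistic. After matching they are -0.02, -0.01 and 0.00.

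The plan also has a hypoglycemia control outcome for the sulfonylurea comparison and a step in Section 11 for listing confounding concerns. Neither adds a covariate. The control-outcome list breaks off in the available text, so nothing can be inferred about further controls.

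**Conclusion.** The gap is real and limited. The score contains no socioeconomic and no preventive-care covariate in any database, and no race in the two commercial ones. The race part is likely small: about 2% or less on the pooled hazard ratio for an assumed R up to 2, and about 4% at R = 3, if the Medicare imbalance carries over. For socioeconomic position and preventive care the documents give neither a prevalence nor a risk ratio, so no percentage can be defended. The matched death ratios (0.63-0.71 against DPP4i, 0.54-0.69 against sulfonylureas, on approximate person-time) are a warning sign that these omissions may matter. They do not show that the omissions caused the gap. Section 13 carries no date, so on the documents the covariates can still be added before the comparative analysis. It is a low-cost improvement and not a reason to reject the design.

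**What to change.** Before the Section 13 analyses are run:

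1. Add baseline-period claims for vaccination, cancer screening and bone density testing to Table 1 and to the score in all three databases.
2. Add Medicare low-income-subsidy or dual-eligibility status, and any plan-type, race or area-level field in Optum and MarketScan, where these are held. List the rest as unavailable and state them as a limitation.
3. Re-match and update the balance and power tables in Sections 9 and 10, correcting the MarketScan and Medicare follow-up rows if they prove to be a copying slip.

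Running the Medicare match with and without race should not be offered as a bound on commercial bias. It needs outcomes, comes from an older population, and says nothing about socioeconomic position.

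The cost is modest programming, possibly slightly fewer pairs, and a repeat of the balance and power review already completed in December 2019. A 180-day window catches only part of services given yearly or less often, so the new markers will reduce the gap without closing it.
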